### 7.7.2 ABOUTTM-Product Experience

Product Experience will be assessed via a subject self-reported outcome measure at V2 and V6 within 60 minutes after the P3P product use for PK assessment, using the ABOUTTM-Product Experience Questionnaire, also part of the ABOUTTM Toolbox (32, 39).

The questionnaire consists of three multi-item scales and two single-item scales, arising from an adaptation and rewording of the modified cigarette evaluation questionnaire (mCEQ) (40) to RRPs and the Product Evaluation Scale (41).

The questionnaire assesses the degree to which subjects experience the reinforcing effects of P3P use by measuring:

- Product satisfaction (satisfying, tastes good, enjoy the product).
- Psychological rewards (calms down, more awake, less irritable, helps concentrate, reduces hunger).
- Aversion (dizziness, nausea).
- Enjoyment of respiratory tract sensations (single-item assessment).
- Craving reduction (single-item assessment).

Subjects will be asked to assess the 12 items of the questionnaire on a 7-point scale, ranging from “not at all” to “extremely”.

### 7.7.3 Sensory Questionnaire

A sensory questionnaire will be completed by each subject at V2 and V6 within 60 minutes after the P3P product use for PK assessment (adapted from (42)). The sensory questionnaire assesses the subject's opinion on the following sensory parameters:

- Puff information i.e., how they liked the puffs, harshness of puffs, and similarity to own brand;
- Strength of puffs on tongue, nose, mouth, windpipe, and chest.

Subjects will be asked to assess the 8 items of the questionnaire on a 7-point scale, ranging from "not at all" to "extremely".

### 7.7.4 Product Acceptance Questionnaire

In the context of tobacco harm reduction, alternative sources of nicotine offered need to be acceptable to smokers as substitutes for cigarettes (43).

At V2 and V6, subjects will complete the product acceptance questionnaire. This questionnaire will be used to assess product characteristics of P3P relevant to determine subjects' acceptability of the product. Subjects will be asked to rate P3P in terms of sensory attributes, ease of use and occasions of use.

A baseline version of the product acceptance questionnaire consisting of 5 questions will be answered at V2, while a 6-questions version containing an additional question asking about occasions of P3P use will be answered at V6.

### 7.7.5 Visual Analogue Scale for Craving

A VAS-craving assessment will be used to assess the level of craving of the subject based on their response to the question, "How strong is your craving for cigarettes?" on a scale of 0 (no craving) to 10 (strong craving) (44).

The VAS craving will be completed multiple times by the subject in relation to the P3P product used for PK assessment at V2 and V6. The first assessment will be done 10 minutes  $\pm$  2 minutes prior to T0. Thereafter in relation to T0, the assessment is to be performed at 4 minutes  $\pm$  2 minutes, at 10 minutes  $\pm$  2 minutes, at 15 minutes  $\pm$  2 minutes, 30 minutes  $\pm$  5 minutes, 1 hour  $\pm$  10 minutes, 2 hours  $\pm$  10 minutes and 4 hours  $\pm$  10 minutes. VAS will be assessed immediately after the collection of the time-matching PK samples.

### 7.7.6 Cough Assessment

At V2-V6, subjects will be asked if they have experienced a regular need to cough, e.g., whether they have coughed several times in the previous 24 hours prior to assessment. If the answer is 'yes', they will be asked to complete a cough assessment questionnaire (which includes a VAS and three Likert scales).

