**Confidentiality Statement**

Data and information contained in this document are considered to constitute trade secrets and confidential commercial information, and the legal protections provided to such trade secrets and confidential information are hereby claimed under the provisions of applicable law. No part of this document may be publicly disclosed without the written consent of Philip Morris Products S.A.

---

4. To assess safety and tolerability during the study.

Endpoints:

- Incidence of adverse events (AEs), serious adverse events (SAEs);
- Frequency of adverse events (AEs), serious adverse events (SAEs);
- Incidence of P3P product events including malfunction/misuse;
- Frequency of P3P product events including malfunction/misuse;
- Physical examination changes from baseline;
- Cough assessment changes from baseline (VAS and three Likert scales) ;
- Electrocardiogram (ECG) changes from baseline (heart rate, PR, QRS, QT, QTcB, QTcF intervals);
- Vital signs changes from baseline (systolic and diastolic blood pressure, pulse rate and respiratory rate);
- Spirometry changes from baseline (FEV1, FEV1 % predicted, FVC, FVC % predicted, FEF 25, FEF 25 % predicted, FEF 75, FEF75 % predicted, FEF 25-75, FEF 25-75 % predicted, FEV1/FVC);
- Changes from baseline in clinical chemistry, hematology, and urinalysis safety panel;
- Concomitant medications.

5. To assess the exposure to harmful and potentially harmful constituents (PHHCs) in spot urine expressed as concentration adjusted for creatinine from Day -1 to Day 30.

Endpoints:

- Biomarker of exposure (BoExp) to nicotine: Nicotine equivalents (NEQ);
- BoExp to NNK: 4-(Methylnitrosamino)-1-(3-pyridyl)-1-butanol (total NNAL);
- BoExp to Acrylonitrile: 2-cyanoethylmercapturic acid (CEMA).

6. To assess tobacco and nicotine containing product dependence at Day -1 and at Day 30.

Endpoint:

- ABOUTTM-Dependence Questionnaire.

7. To assess cytochrome P450 2A6 (CYP2A6) enzymatic activity at Day 1 and at Day 30.

Endpoint:

- Molar metabolic ratio of trans-3'-hydroxycotinine/cotinine in plasma.

8. To estimate the amount of powder extracted from P3P used for PK assessment.

Endpoint:

- Weight difference of P3P before and after use.

[figure not shown]

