#### 6.2.5 Stopping Rules for Investigational Product

For safety purposes, use of P3P should be temporarily reduced (decreasing number or/and intensity of puffs) or stopped in the event of any signs suggesting nicotine overexposure, e.g., gastrointestinal disturbance (nausea, vomiting, diarrhea, stomach or abdominal pain), cold sweats, headache, dizziness and breathing problems, or any other reasons at the discretion of the Investigator. Signs suggesting respiratory disturbance (e.g., wheezing, dyspnoea, chest tightness) which may be related to P3P powder inhalation could also be taken in consideration for P3P reduced use or P3P stopping.

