### Confidentiality Statement

Data and information contained in this document are considered to constitute trade secrets and confidential commercial information, and the legal protections provided to such trade secrets and confidential information are hereby claimed under the provisions of applicable law. No part of this document may be publicly disclosed without the written consent of Philip Morris Products S.A.

Symptoms or worsening of symptoms as documented on any of the questionnaires do not need to be documented as AEs because the questionnaires will be analyzed as part of the report. However, it is at the discretion of the Investigator to document such symptoms also as AEs. The main source for AE collection will be the face-to-face interview between the subject and investigational site staff using, open, non-directive questions (see section 8.2.1).

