**Table 12 Time Schedule – Early Termination**

Blood Sample	Procedures	Additional Information
	Return of used and unused P3P consumables	
✓	Clinical laboratory parameters (hematology, clinical chemistry)	May be done in non-fasting state.
	Urine analysis safety panel	
	Urine pregnancy test (all female subjects)	
	Vital signs (blood pressure, pulse rate, respiratory rate)	At least 5 min in supine position prior to measurement. At least 15 min after P3P use
	ECG	After resting for at least 10 min in supine position prior to recording.
	Spirometry	After resting in sitting position for at least 15 minutes. At least 1 h after P3P use. To be done after vital signs and ECG.
	Physical examination	
	Information on risks of smoking, smoking cessation advice	
	Concomitant disease status check	Provide stop date if available or note ongoing if ongoing at early termination
	AE/SAE, concomitant medication recording	
	Product events malfunctions/misuse	
	Discharge	

Abbreviations: AE = Adverse event; ECG = Electrocardiogram; SAE = Serious adverse event

If a subject withdraws from the study or is discontinued during a planned visit, assessments required as per protocol for early termination that have been already performed during the planned visit should not be conducted again.

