#### Confidentiality Statement

Data and information contained in this document are considered to constitute trade secrets and confidential commercial information, and the legal protections provided to such trade secrets and confidential information are hereby claimed under the provisions of applicable law. No part of this document may be publicly disclosed without the written consent of Philip Morris Products S.A.

	Screening	Admission	Product use period (up to 15 products/day)					Discharge	Early termination	Safety Follow-Up
Visit	1		2		3	4	5	6		
Study day	-22 to -2	-1	1	2	7 ±2d	15 ±2d	22 ±2d	29 ±2d	30 ±2d	+14 days
Sensory Questionnaire			•						•	
VAS Craving p			•						•	
Puffing/inhalation behavior question (assessed by site staff)			•						•	
Puffing/inhalation behavior question (assessed by subject)				•	•	•	•			
Cough assessment (VAS, Likert scale)		•	•		•	•	•	•		
AE/SAE reporting	•	•	•	•	•	•	•	•	•	• q
Concomitant disease status		•			•	•	•			•
P3P product event reporting		•	•	•	•	•	•	•	•	

Abbreviations: ABOUT = Assessment of Behavioral Outcomes related to Tobacco and nicotine products; AE = Adverse event; B = Blood sample; BMI = Body mass index; BoExp = Biomarkers of Exposure; ECG = Electrocardiogram; PK = Pharmacokinetics; SAE = Serious adverse event; U = Urine sample; VAS = Visual analog scale

- a. Prior to enrollment, at Day -1 the following eligibility criteria will be re-checked: Inclusion criteria: smoking status confirmed by urine cotinine, subject is not planning to quit smoking within 2 months, subject is available for the entire study period and is willing to comply with the study procedures. Exclusion criteria: urine pregnancy test (all females), urine drug screen and alcohol breath test. The following eligibility criteria will only be checked at Day -1: Exclusion criteria: subject has received medication which has an impact on CYP2A6 activity within 14 days or within 5 half-lives of the drug prior to Day -1 (whichever is longer)
- b. Pre-study chest X-ray (with anterior-posterior and left lateral views). Available chest computed tomography (CT) or chest magnetic resonance imaging (MRI) results, or radiologist report from an equivalent radiological assessment within 6 months prior to Screening.
- c. Systolic and diastolic blood pressure, pulse rate, and respiratory rate. At V2 (Day -1, Day 1 and Day 2) and V6 (Day 30) vital signs are to be checked prior to any product use and at the end of the day/at discharge.

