12.5.9.5.6 Assessment of Cough

Cough questionnaire is assessed at Day -1, 2, 7, 15, 22, and 29. The number and % of subjects reporting a cough will be summarized by P3P variant. The responses to the individual items, including the VAS evaluating the level of cough bother and 3 Likert scales measuring the intensity, the frequency of cough and the amount of sputum production will be listed and summarized on each day by P3P variant, for all subjects who filled in the questionnaire.

The data will be presented in the below outputs:

TFL number	Title
TABLES	
15.2.32.1	Number and Percentage of Subjects with Cough – Safety Population
15.2.32.2	Summary of VAS Level Cough Bothersome by Timepoint – Safety Population
15.2.32.3	Summary of Intensity, Frequency of Cough and Sputum Production by Timepoint – Safety Population
LISTINGS	
15.1.32.1	Listing of Cough Assessment Results – VAS measurement
15.1.32.2	Listing of Cough Assessment Results - Frequency of Cough and Sputum Production

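### Cough, a secondary safety endpoint, is not assessed at early termination, so subjects who leave the study have no cough value at exit and by-day cough rates may understate cough

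*Protocol*

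**What the plan says.** - **Endpoint.** Protocol 3.2 (objective 4) and SAP 5.2 list change from baseline in cough, by VAS and three Likert scales, among the secondary safety endpoints. Protocol 2.3.3 names cough among the symptoms that P3P users may experience.
- **Schedule.** Protocol 7.7.6: "At V2-V6, subjects will be asked if they have experienced a regular need to cough". The question looks back 24 hours, and the scales are completed only after a yes.
- **Early termination.** Protocol Table 12 ("Time Schedule – Early Termination") repeats laboratory tests, urinalysis, vital signs, ECG, spirometry and physical examination, and includes AE recording. It does not list cough. The text under the table says that assessments already done at a planned visit are not repeated. In Appendix A the cough row has marks at Days -1, 1, 7, 15, 22 and 29 and none under early termination (as far as the extracted columns can be read).
- **Analysis.** SAP 12.5.9.5.6: "Cough questionnaire is assessed at Day -1, 2, 7, 15, 22, and 29". The item scores are "summarized on each day by P3P variant, for all subjects who filled in the questionnaire". There is no early-termination timepoint, whereas the laboratory section (SAP 12.5.9.4) reports Day 30 or early termination.
- **Missing data.** Protocol 12.1.4 does not in general impute, and Protocol 5.2 does not replace subjects who leave after randomization.
- **Adverse events.** Protocol 7.7: "Symptoms or worsening of symptoms as documented on any of the questionnaires do not need to be documented as AEs". The reason given is that the questionnaires are analyzed in their own right.

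**The concern.** P3P is an inhaled powder, and the cough scales are the tolerability measure closest to its route of use. Subjects whose cough is bad enough to make them leave are the ones whose value matters most, and the plan does not collect it at exit. Missingness would then be tied to the outcome. The by-day summaries use whoever is still attending, so they could understate cough and misstate the comparison between variants if dropout differs. Most other safety measures are repeated at early termination, and the documents give no reason for leaving cough out.

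**Working it through.** **Step 1: who has no cough value at exit.**

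- *Product-test leavers.* Table 6 places the Day -1 cough assessment before the product test. Subjects who then decline P3P have early termination the same day (Protocol 4.1). They belong to the Safety population (Protocol 12.3.1, SAP 10.2), and SAP 12.1.3 includes their available data in the safety summaries. Their only cough value precedes exposure.
- *Leavers between Day 1 and V3.* In Table 7 the Day 1 cough assessment falls within 60 minutes after the single PK product, before on-site use of up to 14 more that day. The protocol's next cough assessment is Day 7. The SAP lists Day 2 in place of Day 1.
- *Leavers between later visits.* They have nothing after the last visit attended. If they leave at a planned visit, cough may already have been asked there.

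**Step 2: effect on a by-day percentage.** The plan has no figure to reproduce. The 60 subjects (about 30 per arm) are described as an empirical choice, and no cough rate, dropout rate or power is stated. The inputs below are assumptions. With *n* = 30, *c* subjects who would report cough if all were assessed, and *d* of those leaving first:

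observed rate = (*c* − *d*)/(*n* − *d*)

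| Coughers if all assessed | 1 leaves | 2 leave | 3 leave | 5 leave |
|---|---|---|---|---|
| 3/30 = 10% | 2/29 = 6.9% | 1/28 = 3.6% | 0/27 = 0% | – |
| 6/30 = 20% | 5/29 = 17.2% | 4/28 = 14.3% | 3/27 = 11.1% | 1/25 = 4.0% |
| 9/30 = 30% | 8/29 = 27.6% | 7/28 = 25.0% | 6/27 = 22.2% | 4/25 = 16.0% |
| 12/30 = 40% | 11/29 = 37.9% | 10/28 = 35.7% | 9/27 = 33.3% | 7/25 = 28.0% |

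Each cougher who leaves costs about 2 to 3 points. The SAP does not state the denominator for the percentage reporting cough. With a fixed denominator, three leavers give 6/30 = 20.0%, also low. If three subjects leave and none coughs, the rate rises to 9/27 = 33.3%. With no dropout it is unchanged.

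**Step 3: effect on the variant comparison.** It can go either way.

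- *A difference appears.* Both arms are truly 9/30, and three coughers leave one arm only: 22.2% against 30.0%, a spurious 7.8 points.
- *A difference is hidden.* Stayers cough at 20% and leavers at 60% in both arms; dropout is 10% in one and 20% in the other. The full rates are 0.9 × 20 + 0.1 × 60 = 24% and 0.8 × 20 + 0.2 × 60 = 28%. Both arms show 20%, so a 4-point difference is masked.

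**Step 4: how likely is at least one such leaver?** With probability *p* per subject, 1 − (1 − *p*)^60 is 45%, 84%, 95% and 99.8% for *p* = 1%, 3%, 5% and 10%. These *p* are also assumed.

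**Step 5: would the form alone cure it?** No. By-day percentages stay as they are unless the SAP also uses the exit value. The early-termination visit may fall up to 7 days after discontinuation (Protocol 5.2), so a 24-hour look-back can return a no from someone who left because of cough. The no-repeat rule would also stop product-test leavers from being asked again after exposure.

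**The case against.** The strongest reply is that cough at exit is not lost. Table 12 includes AE recording, and Protocol 8.2.1 requires every AE to be documented. The AE record carries intensity (Table 3) and relatedness (8.2.4). SAP 12.5.9.2 tabulates AEs leading to product and study discontinuation by preferred term, and Protocol 12.6.3 makes AE data the primary assessment of safety. The discretion in Protocol 7.7 covers symptoms written on a questionnaire, so it does not formally reach a cough reported at an exit interview where no questionnaire is given. This stands: cough can be captured at exit. It is captured through open questions, however, not the prompted question, and it yields no VAS or Likert change from baseline.

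A reader might also infer that anyone who stops the powder because of cough drops out of the cough data. The documents do not support that. Subjects may stop P3P at any time during the study (Protocol 6.2), and stopping product after randomization is not itself a listed reason for discontinuation (5.2). Subjects who quit nicotine altogether still attend all visits for safety assessments (2.3.1). All who stay are asked about cough at V3 to V6. Section 6.2.5 does not close this gap: it speaks of signs "which may be related to P3P powder inhalation could also be taken in consideration for P3P reduced use or P3P stopping", which concerns product use and not study exit, and its respiratory examples do not include cough.

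Finally, the study is descriptive, no test on cough is planned, and four points is about one subject in 30.

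**Conclusion.** The gap is real and holds for a defined group: subjects who leave the study between visits, and those who leave after the product test. They have no cough endpoint value at exit, and VAS and Likert severity cannot be recovered from the AE record.

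A reader might go further and say that later cough rates are biased low. That is conditional. It needs cough-related study dropout, for which the documents give no rate. It also depends on the target: a subject off the powder might no longer cough by Day 29, so the understatement is clearest for the rate under continued use. Nor does unequal dropout by itself create a variant difference; it can mask one as easily, as Step 3 shows. The low by-day rates would come from observed-case summaries, not from the missing form alone.

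Under the assumed range (10% to 40% coughing, one to five coughers leaving an arm of 30), the understatement runs from about 2 to 16 points. It is zero if nobody leaves because of cough. The change is worth making because the endpoint is named, the effect is anticipated and the remedy is small.

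**What to change.** **Protocol.** Add the cough question and, after a yes, the VAS and three Likert scales to Table 12 and to the early-termination column of Appendix A. Word the question so that it also covers the 24 hours before last P3P use or discontinuation. Exempt it from the no-repeat rule when that day's earlier cough assessment preceded P3P exposure.

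**SAP 12.5.9.5.6.** Add a per-variant summary of any regular cough, and of the worst VAS and Likert scores, at any post-exposure assessment including early termination. Show non-randomized product-test leavers in the overall column. State the denominator of the cough percentages. Even without the new form, this summary would keep subjects who reported cough at a visit before leaving.

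**Reconcile** the early cough day: Day 1 in Protocol Table 7 and Appendix A, Day 2 in the SAP.

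**Cost.** A short amendment, one existing form (one question and at most four items) at an existing visit, a slightly longer recall for leavers, and one extra table. No added visit is needed.

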#### Confidentiality Statement

Data and information contained in this document are considered to constitute trade secrets and confidential commercial information, and the legal protections provided to such trade secrets and confidential information are hereby claimed under the provisions of applicable law. No part of this document may be publicly disclosed without the written consent of Philip Morris Products S.A.

The VAS will assess how bothersome cough is to the subject, on a 10 cm scale ranging from 'not bothering me at all' to 'extremely bothersome'.

Furthermore, subjects will be asked to assess the intensity and frequency of cough and the amount of sputum production on Likert scales:

- The intensity of cough will be assessed on a 5-point Likert scale ranging from 1 to 5:  
1 = very mild; 2 = mild; 3 = moderate; 4 = severe; 5 = very severe.
- The frequency of cough will be assessed on a 5-point Likert scale ranging from 1 to 5:  
1 = rarely; 2 = sometimes; 3 = fairly often; 4 = often; 5 = almost always.
- The amount of sputum production will be assessed on a 4-point Likert scale ranging from 0 to 3:  
0 = no sputum; 1 = a moderate amount of sputum; 2 = a larger amount of sputum; 3 = a very large amount of sputum.

## 7.8 Other Study Procedures

### 7.8.1 Product Use Diary

Subjects will enter the number of P3P consumables used per day, the number of cigarettes used per day, or/and other tobacco and nicotine containing products used per day in a product use diary from Day 1 (V2) until the Discharge at V6 (including during the visits). At V2, before they start using it, subjects will be trained on how to log into the designated website and complete the product use diary by site staff. For subjects who decide to quit using all tobacco and nicotine containing products the product use will no longer be captured.

Site staff should train the subject on the correct use of the subject diary and perform regular checks to ensure that the subject completes the diary in the frequency and the way required.

### 7.8.2 Puffing/inhalation behavior question

At V2 (Day 1) and V6 (Day 30), during the use of P3P for PK assessment the site staff will be asked to observe the puffing/inhalation behaviour of the subjects and answer a question related to it. The staff will evaluate if the subject is using P3P by:

- puffing and holding the aerosol in the mouth for a short time and then inhaling (i.e. like a cigarette);
- puffing and immediately inhaling (without holding the aerosol in the mouth); or
- puffing and immediately exhaling, without inhalation;

At V2 (Day 2), V3, V4, V5, V6 (Day 29), the subjects will also answer the same question about their own puffing/inhalation behaviour.

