One pharmacokinetic clinical study was conducted with P3P in 19 smokers in Switzerland (ClinTrials.gov: NCT03369340). In this study, following a single use of four P3P variants, nicotine  $C_{max}$  was 1.1 ng/mL for the 1 mg variant and between 2.1 and 3.1 ng/mL for the 2 mg variants and was reached after 15-22.5 minutes ( $T_{max}$ ).  $C_{max}$  values for P3P were lower compared to literature-reported  $C_{max}$  for cigarettes which ranges between 10-30 ng/mL (23-25) or Nicorette® Inhalator, a nicotine replacement therapy, for which  $C_{max}$  values of 6-8 ng/mL have been described (25, 26).  $T_{max}$  was at a later timepoint for P3P compared to cigarettes for which maximal plasma concentration is reached after 5-8 minutes, but earlier compared to Nicorette® Inhalator for which  $T_{max}$  is at 30 minutes. Thus, the observed concentration-time profile for P3P is indicative of a partial pulmonary and partial oromucosal absorption compared to the pulmonary absorption for cigarettes and the oromucosal absorption of Nicorette® inhalator. The adaptation of the product use behavior in these subjects, which were unfamiliar with P3P may have been incomplete. The product was generally well tolerated and no safety concern was revealed.

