## 2.2 Purpose of the Study

The purpose of the study is to evaluate the adaptation of product use in adult, current cigarette smoking subjects between baseline and after 1 month of use of one of two P3P variants.

The effect of P3P use behavior on nicotine pharmacokinetic (PK) profile, acceptability, as well as the safety and tolerability of P3P over a period of 1 month will be investigated. In addition, the overall use of tobacco and nicotine containing products will be monitored.

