12.5.8 Weighing of P3P Products

For each timepoint (Day 1 and Day 30), the weight difference of P3P before and after use will be derived and presented by P3P variant, by sex and by product exposure category.

The data will be presented in the below outputs:

TFL number	Title
TABLES	
15.2.22.1	Descriptive Statistics of Weight of P3P before and after use – Day 1 and Day 30 - PK Population
15.2.22.2	Descriptive Statistics of Weight P3P of before and after use – Day 1 and Day 30 – By Sex - PK Population
15.2.22.3	Descriptive Statistics of Weight of P3P before and after use – Day 1 and Day 30 – By Product Exposure Category - PK Population
FIGURES	
15.3.4.1	Scatter Plot of PK AUC _(0-4h) versus P3P Weight difference By Puffing Behavior – Day 1 and Day 30 – PK Population
LISTINGS	
15.1.22.1	Listing Results of Weight of P3P before and after use – Day 1 and Day 30

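### The puffing/inhalation question has no answer for holding the aerosol in the mouth and exhaling without inhaling, so a later start of inhalation can be hidden, depending on a rater choice that neither document specifies

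*Protocol*

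**What the plan says.** Protocol 7.8.2 asks site staff to classify each subject's use of the PK product on Day 1 and Day 30. The answers, labelled here A to C, are:

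- **A**: "puffing and holding the aerosol in the mouth for a short time and then inhaling (i.e. like a cigarette")
- **B**: "puffing and immediately inhaling (without holding the aerosol in the mouth")
- **C**: "puffing and immediately exhaling, without inhalation"

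On Day 2, at V3 to V5 and on Day 29, "the subjects will also answer the same question about their own puffing/inhalation behaviour". SAP 7.3.2 repeats the three answers and sets separate baselines: Day 1 for staff ratings and Day 2 for subject ratings. Protocol 7.8.2 promises training for staff and subjects on how to make the evaluation.

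SAP 12.5.3.2 plans descriptive tables 15.2.17.1 to 15.2.17.6. Two of these are shift tables: 15.2.17.2 (staff, Day 1 to Day 30) and 15.2.17.4 (subjects, Day 2 to Days 7, 15, 22 and 29). SAP 12.5.8 also plans Figure 15.3.4.1, a scatter plot of AUC against "P3P Weight difference By Puffing Behavior".

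**The concern.** Two features define the answers: whether the aerosol is held in the mouth, and whether it is inhaled. The only answer with holding requires inhaling, and the only answer without inhaling requires exhaling at once. A subject who holds and then exhales fits neither, and the two nearest answers disagree on whether inhalation took place.

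This bears on what the study is for. Protocol 2.2 states: "The purpose of the study is to evaluate the adaptation of product use in adult, current cigarette smoking subjects". Protocol 4.2 explains that PK is repeated on Day 30 because a change in puffing or inhalation may alter the absorption phase. Starting to inhale is one such change, and the shift tables are where a reader would look for it. A pattern that the form cannot record cannot be recovered at analysis.

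**Working it through.** The plan states no figure on this point, so the check is an enumeration.

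**Step 1: answers against the two features** (Protocol 7.8.2; SAP 7.3.2 is identical).

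| | Inhaled | Not inhaled |
|---|---|---|
| Held in mouth | A | no answer |
| Not held | B | C |

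The list covers 3 of 2 × 2 = 4 combinations. Neither document gives an open category or a rule for the empty cell.

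**Step 2: a subject who holds and exhales at baseline and later inhales.** The baseline rating must be A (right on holding, wrong on inhalation) or C (right on inhalation, wrong on holding). The later behaviour is truly A or B and can be coded correctly. That gives 2 × 2 = 4 paths.

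| Baseline code | Later code | Shift table shows | Start of inhalation visible? |
|---|---|---|---|
| A | A | no change | no |
| A | B | move between two inhaling patterns | no |
| C | A | no inhalation to inhalation | yes |
| C | B | no inhalation to inhalation | yes |

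One path of four shows no change, and two of four hide the start of inhalation. These are counts of paths, not probabilities. The documents do not say how often the pattern occurs or how raters would code it.

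The same reasoning applies within Table 15.2.17.2 for staff and within Table 15.2.17.4 for subjects. The two rater types have separate baselines and separate tables, so disagreement between staff and subjects does not enter either one.

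**Step 3: the figure.** A subject coded A under Step 2 would be plotted with the inhaling group in Figure 15.3.4.1 although that subject did not inhale.

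**Step 4: after the change.** With a fourth answer D for the empty cell, the two true moves are D to A and D to B. Both lie off the diagonal, and 2 of 2 show the start of inhalation. If instead C is reworded to cover all non-inhaling use, the moves become C to A and C to B, and again 2 of 2 are visible. In that case holding among non-inhalers is no longer distinguished.

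**Step 5: reach.** The models for the primary PK parameters in SAP 12.5.1 use variant, sex and, for the Day 30 comparison, the Day 1 value. The puffing answer enters none of them.

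**The case against.** The strongest reply is that C is the more natural choice. It is the only answer that rules out inhalation. Choosing A means contradicting its central feature, whereas choosing C means overlooking only the requirement that exhaling be immediate. Coded as C, a later start of inhalation is recorded correctly. This stands, and it makes the loss conditional. It does not remove the loss, because no document tells raters to choose C.

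Training is the stated safeguard and could produce consistent coding. It cannot add an answer that the form lacks, and no rule for this pattern is written down. The eCRF and the training material are not among the documents, so an instruction or an open field there cannot be excluded.

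A reader might infer three stronger points that the documents do not support:

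- **That hold-and-exhale is the source of oromucosal uptake.** Protocol 2.1.2 and 4.2 describe the earlier PK profile as "indicative of a partial pulmonary and partial oromucosal absorption" but tie it to no puffing pattern. Answer A also involves holding in the mouth, and no passage reports that anyone holds and exhales.
- **That this question is the study's only measure of use behaviour.** Start and stop times of the PK product use (Protocol 6.2.2), daily product counts (7.8.1) and the product's weight loss (7.8.3) are also recorded. None of these shows whether the aerosol was inhaled, so the narrower claim holds: this is the only record of inhalation pattern.
- **That the distortion of AUC by category can be sized.** The documents give no frequency for the pattern and no AUC contrast between inhalers and non-inhalers. The SAP plans a scatter plot, not a mean or ratio of AUC by puffing category.

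**Conclusion.** The gap is real and identical in both documents: three of four combinations are covered, and holding followed by exhaling without inhaling has no correct answer. The consequence is conditional. If raters use A for this pattern, a later start of inhalation is hidden in Table 15.2.17.2 or 15.2.17.4, and a non-inhaler is shown among inhalers in Figure 15.3.4.1. If they use C, the start of inhalation is recorded and only the holding is lost.

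The number of subjects affected is unknown and could be none. The endpoint is secondary and descriptive, and the primary PK estimates do not depend on it; only their interpretation by inhalation pattern does. The conclusion assumes that the forms carry the three answers as listed, with no further instruction. On that basis it is a modest but worthwhile improvement to a measure that bears directly on adaptation of use.

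**What to change.** In Protocol 7.8.2 and SAP 7.3.2, add a fourth answer to the staff and subject forms: *holding the aerosol in the mouth and then exhaling, without inhalation*. Carry the four categories into Tables 15.2.17.1 to 15.2.17.6 and Figure 15.3.4.1.

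At minimum, delete the word *immediately* from the third answer so that it covers all non-inhaling use. This makes the start of inhalation visible without adding a category, but it gives up the distinction between holding and not holding among non-inhalers.

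The full change costs one answer line on each form and revised category wording in the SAP outputs. The downside is one more category, possibly sparse, in arms of about 30.
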